### 9.4 STATISTICAL ANALYSES

#### 9.4.1 GENERAL APPROACH

Descriptive analyses will be calculated for all variables. We will compare the two study groups on baseline variables to assess whether balance was achieved through the randomization. Changes from pretest to 1-month follow-up on continuous primary and secondary outcome variables will be compared between groups using t-tests. Binary primary and secondary outcome variables (outcome improved vs. not improved) will be compared between groups using Chi-tests.

Group differences on change in physical activity (i.e., metabolic equivalents, number of days 60 minutes or more of physical activity), and diet (number of fruits and vegetables, junk food, sugar-sweetened beverages consumed per week), as well as the standard deviations of the changes in each group, will be used to calculate sample size for the next study.

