### 6.3 MEASURES TO MINIMIZE BIAS: RANDOMIZATION AND BLINDING

Masking is not applicable to the study design. Participants will be randomized to conditions upon enrollment with the goal of balancing the number of participants in each condition (e.g., 1st participant assigned to condition 1, 2nd to condition 2, 3rd to condition 1).

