### 9.2 SAMPLE SIZE DETERMINATION

This is a feasibility pilot study, therefore the sample size was not determined via power calculations.

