### 9.3 POPULATIONS FOR ANALYSES

Intention-to-Treat (ITT) analysis population (i.e., all randomized participants).

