#### 10.1.4 FUTURE USE OF STORED SPECIMENS AND DATA

Data collected for this study will be analyzed and stored at CUNY SPH. Due to the small sample size that increases the identifiability of participants, data will not be stored at a repository.

---

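### The change-score t-test in 9.4.1 is valid but fixes the pretest slope at 1; a linear model with the pretest value as covariate would usually be more precise and would correct for chance pretest imbalance, at a cost of one degree of freedom.

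*Combined protocol and SAP*

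**What the plan says.** Section 9.4.1 sets the analysis of continuous outcomes in one sentence: "Changes from pretest to 1-month follow-up on continuous primary and secondary outcome variables will be compared between groups using t-tests". Baseline enters in one other place: "We will compare the two study groups on baseline variables to assess whether balance was achieved through the randomization". No action is attached to the result of that comparison. No regression, mixed model or other baseline adjustment appears anywhere in the document.

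The covariate is already collected. The schedule in 1.2 puts a pretest survey with all outcome measures in Week 2, before the modules start in Week 3, and the 1-month follow-up in Week 12.

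Section 9.2 explains why there is no power figure: "This is a feasibility pilot study, therefore the sample size was not determined via power calculations". No sample size is given; 10.1.4 says only that the sample is small. Section 4.2 says the results will feed the power calculation for a full-scale trial, and 9.4.1 says how: the group differences on change, "as well as the standard deviations of the changes in each group, will be used to calculate sample size for the next study".

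**The concern.** Subtracting the pretest value does use it, but with a coefficient fixed at 1. That is the best choice only if the regression slope of follow-up on pretest is 1. The diet and activity outcomes in 8.1 are self-reports that recall the past 7 days or the past 7 to 30 days, repeated about 10 weeks apart. A slope below 1 is therefore likely, though the documents give no figure for it. With a slope below 1, the change score carries pretest noise into the comparison, and the arm that happens to start higher will tend to show less gain.

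Two things are at stake: the precision of the arm comparison that 9.1 sets up as the primary hypothesis, and the quality of the effect estimates and SDs handed to the next study.

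**Working it through.** **Inputs.** From the documents: the t-test on change (9.4.1), pretest values for all outcomes (1.2), roughly equal arms (6.3), and no N, SD or correlation (9.2 gives none). Assumed: rho from 0.3 to 0.9; equal SDs at both times unless stated; 30 per arm where a sample size is needed.

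The plan states no figure on this point, so there is none to reproduce.

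**Step 1: variance formulas.** Let the pretest SD be 1, the follow-up SD be k and the correlation be rho. The slope of follow-up on pretest is rho × k. Per participant:

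- variance of change = 1 + k² − 2 × rho × k
- ANCOVA residual variance = k² × (1 − rho²)
- the first minus the second = (1 − rho × k)², which is zero only at slope 1

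**Step 2: equal SDs (k = 1).** The variances become 2(1 − rho) and 1 − rho², with ratio (1 + rho)/2.

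| rho | change | ANCOVA | ratio | reduction in SE | extra participants needed with change scores |
|---|---|---|---|---|---|
| 0.3 | 1.40 | 0.91 | 0.65 | 19% | 54% |
| 0.5 | 1.00 | 0.75 | 0.75 | 13% | 33% |
| 0.7 | 0.60 | 0.51 | 0.85 | 8% | 18% |
| 0.9 | 0.20 | 0.19 | 0.95 | 3% | 5% |

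The reduction in SE is 1 − √ratio. The last column is 2/(1 + rho) − 1.

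**Step 3: cost of estimating the slope.** The ANCOVA variance is inflated by about 1 + 1/(2n − 4), with n per arm. At 30 per arm this is 1 + 1/56 = 1.018. A simulation with 30 per arm and 40,000 replicates gave ratios of 0.67, 0.77 and 0.86 at rho 0.3, 0.5 and 0.7. These are about 2 percentage points less favourable than the table, and they turn the 54%, 33% and 18% into about 49%, 30% and 16%. With equal SDs, the gain vanishes only above rho 0.965 at 30 per arm (2/1.018 − 1) and above 0.946 at 20 per arm (2/1.028 − 1).

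**Step 4: unequal SDs.** At rho 0.7 and k = 1.2:

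- change variance = 1 + 1.44 − 1.68 = 0.76
- ANCOVA variance = 1.44 × 0.51 = 0.734
- ratio = 0.97, against 0.85 with equal SDs

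At rho 0.7 and k = 0.8:

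- change variance = 1 + 0.64 − 1.12 = 0.52
- ANCOVA variance = 0.64 × 0.51 = 0.326
- ratio = 0.63

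So the figures in Step 2 can move either way.

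**Step 5: chance imbalance.** Given a pretest difference d between arms, the change-score estimate shifts by −(1 − slope) × d. With equal SDs, rho 0.5 and d = 0.2 SD, the shift is −0.5 × 0.2 = −0.10 SD. At 30 per arm the SD of d is √(2/30) = 0.26, so an imbalance of 0.2 is ordinary. In simulated trials with d near 0.3, the change-score estimate shifted by −0.20, −0.16 and −0.09 SD at rho 0.3, 0.5 and 0.7 (formula: −0.21, −0.15, −0.09). The ANCOVA estimate shifted by less than 0.01 SD. Over all simulated trials both estimates averaged close to zero, as they should with no true effect.

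**Step 6: what passes to the next study.** If that study uses ANCOVA but is sized on the SD of change, its N is too large by the factor 2/(1 + rho): 1.54, 1.33, 1.18 and 1.05 at the four correlations, with equal SDs.

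**The case against.** The strongest reply is that nothing here is invalid and little depends on it. This is a pilot with no stated power, alpha or N, so no stated figure is undermined. The SD of change is the right planning input if the next study also analyses change; if that study uses ANCOVA, sizing on the SD of change errs on the conservative side. Every figure for the gain rests on an assumed rho, an assumed N and equal SDs. The argument for a modest rho comes from the self-reported outcomes and does not carry over to the health literacy measures, which 8.1 describes as objective. All of this stands. It limits the size of the point and how certain that size is, but it does not remove the point, because the estimates are meant to be used and the better analysis needs no new data.

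Three stronger readings are tempting, and the documents do not support them:

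- **That the planned t-test is biased or invalid.** Under proper randomization it is neither. The 0.10 SD shift is conditional on one realised imbalance, and the change-score standard error already allows for such variation across randomizations.
- **That adjustment would repair the allocation.** The example in 6.3 ("e.g., 1st participant assigned to condition 1, 2nd to condition 2, 3rd to condition 1") describes alternation. If assignment is predictable, imbalance need not be due to chance, and pretest adjustment does not cure that bias. It is a separate issue.
- **That site should be added to the model as well.** The number of sites is not given, and 6.3 does not describe allocation stratified by site. Site terms could use up degrees of freedom that a small sample cannot spare.

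**Conclusion.** The point holds as a matter of efficiency and of sensitivity to chance imbalance, not of validity. With equal SDs, ANCOVA brings the variance to 0.65–0.85 of the change-score variance for rho 0.3 to 0.7, or 0.67–0.86 at an assumed 30 per arm, and to about 0.95 at rho 0.9. The gain is smaller if the follow-up SD moderately exceeds the pretest SD, and larger if it falls below it. The conditional shift is about half the pretest imbalance when the slope is 0.5. Rho, N and the SDs are all assumptions, since the documents give none of them. This is a low-cost improvement worth making, because 4.2 and 9.4.1 give the pilot's estimates a job in sizing the next trial.

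**What to change.** In 9.4.1, replace the t-test sentence with: *Each continuous outcome at 1-month follow-up is analysed by a linear model with arm and the pretest value of that outcome; the adjusted mean difference with 95% CI is reported.*

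In the paragraph on sizing the next study, add that the residual SD from this model and the pretest-to-follow-up correlation will be reported for each outcome alongside the SD of change. The next study can then be sized for either analysis.

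The cost is one degree of freedom per model and a few lines of code. There is no new data collection: both analyses need the same two measurements from each participant, so the population defined in 9.3 is unaffected.

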### 2.2 BACKGROUND

The rates of pediatric obesity (~19%) and diabetes (0.24%) in the US are alarming and behaviors implicated in obesity and type 2 diabetes are highly prevalent. Approximately 69% and 73% of adolescents consume less than two fruits and vegetables daily respectively, while 53% engage in insufficient physical activity. These behaviors magnify adolescents' immediate and long-term risks for obesity and obesity-related chronic illnesses, as well as complicate the treatment of obesity-related chronic illnesses. Children and adolescents who are obese are four times more likely to be diagnosed with type 2 diabetes than normal weight children, with serious short and long-term consequences impacting quality of life. Reduced life expectancy is the future of America's youth if behavioral changes are not implemented to improve health and reduce the obesity burden. Reversing current national trends in obesity and type 2 diabetes require novel and sustainable prevention strategies to address children and adolescents' obesogenic behaviors.

Adolescence is marked by increased autonomy in decision-making, yet data suggest that adolescents are not equipped with all the skills to make effective health-related behavioral decisions. While health knowledge works in conjunction with motivation and behavioral skills to predict behavior, most existing adolescent interventions target these variables in isolation with modest success. Researchers have argued that health literacy (HL) – the ability to access, understand, and use health information to make informed health decisions – is a precursor to health knowledge and is necessary for translating health knowledge into behavior. Low HL among adults is associated with poor ability to interpret health messages, and results in reduced preventive health behaviors. Further, parent and adolescent HL is negatively related to adolescents' obesity status. Thus, while research on adding HL to existing behavior interventions to improve adolescents' obesity prevention behaviors is lacking, it is expected that the inclusion of HL into existing interventions will increase intervention effectiveness and positive behavior outcomes.

The long-term goal of this line of research is to reduce the incidence of obesity in adolescents and by extension reduce the risk for obesity-related chronic illnesses using interventions that address individual

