## 5 STUDY POPULATION

### 5.1 INCLUSION CRITERIA

Adolescents 13-16 years old at time of enrollment (may turn age 17 during the study)  
Must have parental consent  
All weight classifications

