## 8 STUDY ASSESSMENTS AND PROCEDURES

### 8.1 ENDPOINT AND OTHER NON-SAFETY ASSESSMENTS

*Primary outcomes.* The primary outcomes of the study are the obesogenic behaviors that are expected to change as a result of participation in the intervention including:

- Diet: Within diet, we are interested in both healthy eating (e.g., fruits and vegetables, whole grain, fiber, calcium) and unhealthy eating (sugary and salty foods, fast foods, sugar-sweetened beverages, saturated fats) (healthy and unhealthy). The Dietary Screener Questionnaire and National Youth Physical Activity and Nutrition Study survey, two measures widely used in diet and obesity-related research with acceptable reliability and validity will be used to assess diet. These questionnaires assess frequency of intake in the past 7-30 days.
- Activity: Both physical activity and sedentary activity will be assessed. The Youth Activity Profile is a 15-item questionnaire designed to assess physical activity and sedentary behavior in youth. This self-report measure has been cross-validated with objective measures of physical activity and resulted in similar group estimates acquired from objective measures. The Godin and Shephard Leisure-Time Physical Activity Questionnaire is a 3-item self-report assessment of leisure time physical activity and provides corresponding metabolic equivalents. Both measures provide minutes in activity and use a 7-day recall.

*Secondary outcomes.* The secondary outcomes of the study is change in health literacy.

- Four types of health literacy will be assessed. Functional, interactive, and critical health literacy will be assessed using an objective measure, the Adolescent Assessments of Health Literacy. Media health literacy will be measured using an objective measure, Adolescent Media Health Literacy Scale.

All assessments are validated and will be scored per the test authors' scoring guidelines.

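### Section 9.4.1 tests an undefined improved/not-improved split by chi-square beside t-tests on change, with no lead test named and no rule for adolescents already at the best level

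*Combined protocol and SAP*

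**What the plan says.** Section 9.4.1 (General Approach) sets out two comparisons between arms. The first is for continuous outcomes: "Changes from pretest to 1-month follow-up on continuous primary and secondary outcome variables will be compared between groups using t-tests". The second is for binary outcomes: "Binary primary and secondary outcome variables (outcome improved vs. not improved) will be compared between groups using Chi-tests". Neither uses the pretest value as a covariate. The section does not list the binary outcomes, say whether they are derived from scores that also receive a t-test, define how much change is improvement, or rank the two tests. It ends by sizing the next study from group differences in change and the SDs of change, on the continuous scale.

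Section 8.1 gives the outcome scales. For diet: "These questionnaires assess frequency of intake in the past 7-30 days". For activity: "Both measures provide minutes in activity and use a 7-day recall". Health literacy comes from scored objective instruments. Section 9.4.1 also names "number of days 60 minutes or more of physical activity" and weekly sugar-sweetened beverages among the outcomes.

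Sections 5.1 and 5.2 set no minimum level of risk behaviour for entry. On weight, Section 5.1 admits "All weight classifications".

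Section 9.2 states: "This is a feasibility pilot study, therefore the sample size was not determined via power calculations". No number of participants is given.

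**The concern.** No outcome in Section 8.1 is described as binary, so improved/not improved looks like a finer score reduced to two categories. This has three consequences.

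- **Meaning.** A bounded outcome leaves some participants no room to improve. An adolescent who starts at 7 active days and stays there is classed with one who falls from 7 to 2. In a prevention trial, holding the best behaviour is a success, yet the wording scores it as a non-success.
- **Precision.** Where the binary is the only or the leading test, a small gain counts the same as a large one, and the comparison is usually weaker.
- **Multiplicity of reading.** Where both tests are run on one outcome, there are two answers and no rule for which one counts.

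The second and third are alternatives for any given outcome. The documents do not say which applies.

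**Working it through.** The documents state no sample size, alpha, effect size, SD, response rate or share at a bound, so there is no figure of the plan's own to reproduce. Everything numerical below is illustrative. It assumes two-sided alpha 0.05, 80% power and 1:1 allocation (Section 6.3 aims for balance).

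**1. Ceiling and floor, from the wording alone.** With a 7-day recall, active days cannot exceed 7, and beverages per week cannot fall below 0. For a participant at either bound, change in the good direction is impossible, so improved is impossible. Sections 5.1 and 5.2 do not keep such participants out. This step needs no distributional assumption.

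**2. Information lost by the cut.** For a location shift, the efficiency of the binary comparison relative to the comparison of means is σ²f(c)²/[p(1−p)]. Here p is the share improved in the comparison arm and f(c) is the density of change at the cut. For normal change:

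- p = 0.5: 0.3989²/0.25 = 0.637, a loss of 36.3%
- p = 0.3: 0.3477²/0.21 = 0.576, a loss of 42.4%
- p = 0.2: 0.2800²/0.16 = 0.490, a loss of 51.0%

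On ordered items an unchanged answer counts as not improved, which can push p below 0.5.

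**3. Dependence on the shape of change.** The same formula gives these relative efficiencies:

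| Distribution of change | p = 0.5 | p = 0.2 |
|---|---|---|
| Normal | 0.64 | 0.49 |
| Logistic | 0.82 | 0.53 |
| t, 5 df | 0.96 | 0.59 |
| t, 3 df | 1.62 | 0.84 |
| Laplace | 2.00 | 0.50 |
| Uniform | 0.33 | 0.52 |

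At p = 0.5 the result runs from a 67% loss to a gain.

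**4. Finite samples, normal change, d = 0.5 assumed.** On the continuous scale, n per arm = 2(1.960 + 0.842)²/0.5² = 62.8, so 63. For the binary with p = 0.5, the other arm has Φ(0.5) = 0.691 and needs 102 per arm. At p = 0.3 it is 103, and at p = 0.2 it is 115. With p = 0.5, power by normal approximation is 49% against 32% at 30 per arm, and 70% against 50% at 50 per arm.

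**5. Dilution by a ceiling.** Suppose 40% and 60% improve among those able to. If a share s starts at the bound, both rates are multiplied by (1−s):

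- s = 0: 40% against 60%, 97 per arm
- s = 10%: 36% against 54%, 119 per arm
- s = 20%: 32% against 48%, 146 per arm
- s = 30%: 28% against 42%, 182 per arm

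The t-test also suffers, but less. In a simulated 0–7 day outcome (100 per arm, 0.75-day effect before rounding and truncation, means and SDs assumed), power was 78% for the t-test and 61% for chi-square with 7% at the ceiling. With 31% at the ceiling it was 66% and 39%.

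**6. Is chance baseline imbalance a fault of the cut?** Take no effect, a pretest–follow-up correlation of 0.5 and an imbalance of 0.2 SD. The SD of change is √[2(1−0.5)] = 1, and the spurious mean change is (0.5−1)(0.2) = −0.1. Improved rates are then 50% and Φ(−0.1) = 46%. At 30 per arm the t-test shifts by 0.1/√(2/30) = 0.39 SE. The two-proportion test shifts by 0.040/√(0.5/30) = 0.31 SE. The planned t-test is disturbed at least as much, so the cause is the missing pretest adjustment, which both tests share.

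**The case against.** The strongest reply is that the plan keeps the continuous analysis. The sentence just before the chi-square sentence compares continuous change by t-test, and the next trial is to be sized from continuous differences and SDs. Section 4.2 gives the purpose as preliminary efficacy and powering a full-scale trial, so the information needed for sizing is retained. This stands. A reader might infer that the plan as a whole throws away over a third of its information. The documents do not support that, because the loss arises only for outcomes analysed solely or mainly as binary.

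Three further points also stand.

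- The 36% figure is normal theory, and normality is doubtful for weekly counts of junk food or sugary drinks.
- The documents give no share at a bound. Section 2.2 reports "Approximately 69% and 73% of adolescents consume less than two fruits and vegetables daily respectively, while 53% engage in insufficient physical activity". The complements (31%, 27% and 47%) are background rates of passing a threshold. They do not show how many enrolled adolescents would start at the best level. Minutes and metabolic equivalents have no evident ceiling, and entry at any weight says nothing direct about behaviour scores.
- Loss of power weighs less in a pilot that was not sized on power.

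The reply leaves three gaps. Section 9.4.1 still does not identify the binary outcomes, rank the tests, or deal with participants who cannot improve. The pilot label does not remove the need, since Section 9.1 states a between-arm efficacy hypothesis.

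**Conclusion.** The point holds in a limited form and should be corrected.

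- **Firm, from the text:** improved is undefined, the binary outcomes are unnamed, no test leads, and an adolescent at a ceiling or floor at pretest can only be classed as not improved. That the binary is a cut of change from pretest is an inference from Section 8.1, though the natural one.
- **Conditional:** for an outcome judged on the binary, the loss is about 36% or more if change is roughly normal. It is smaller, or becomes a gain, for some heavy-tailed distributions. For an outcome given both tests, the harm is two unranked results that may conflict.
- **Illustrative only:** all power and sample-size figures, since n, effect size, correlation and share at a bound are assumed.

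A reader might also infer that the cut is what exposes the result to baseline imbalance. It is not: the t-test on change has the same weakness, slightly larger in the example. The cut does not affect the continuous t-tests or the planned sizing of the next trial, but those t-tests do ignore the pretest value.

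**What to change.** In Section 9.4.1:

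1. Make the lead analysis of each primary and secondary outcome a comparison of the 1-month score between arms with the pretest value as covariate. Where suitable, use an ordinal model with pretest category as covariate for ordered frequency items.
2. Demote improved/not improved to a descriptive summary: the proportion in each arm with a 95% CI and no formal test.
3. Name the outcomes summarised this way, define the change that counts as improvement, and state how participants at a ceiling or floor at pretest are counted, for example by showing them as a separate category.

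The group differences and SDs of change can still be reported for sizing the next study.

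The cost is SAP wording. The pretest and 1-month surveys in Section 1.2 already supply the data, so no visit or instrument changes. The downside is that a simple percent-improved comparison is no longer a formal test. The ordinal model also brings its own assumptions and may need sparse categories merged in a small pilot.

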### 4.2 SCIENTIFIC RATIONALE FOR STUDY DESIGN

This study design will allow for determining the preliminary efficacy of the intervention and the results will be used to calculate power for a full-scale trial.

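### Sizing the next trial on the observed pilot differences makes its sample size very unstable and its expected power lower than planned

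*Combined protocol and SAP*

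**What the plan says.** The last paragraph of Section 9.4.1 begins "Group differences on change in physical activity" and goes on to diet. It names five measures: metabolic equivalents, days with at least an hour of activity, fruit and vegetables, junk food, and sugar-sweetened beverages. The observed differences on these, "as well as the standard deviations of the changes in each group, will be used to calculate sample size for the next study".

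Section 4.2 says the same in general terms: "the results will be used to calculate power for a full-scale trial".

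On the pilot's own size, Section 9.2 says that "the sample size was not determined via power calculations". Section 10.1.4 gives the only other indication: "Due to the small sample size that increases the identifiability of participants". Section 6.3 randomises "with the goal of balancing the number of participants in each condition", so equal arms are intended. The analysis behind the differences is also in Section 9.4.1: "Changes from pretest to 1-month follow-up on continuous primary and secondary outcome variables will be compared between groups using t-tests".

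The documents give no smallest worthwhile difference, no confidence limit or shrinkage for the observed difference, no rule for deciding whether to proceed, and no statement of which of the five measures sizes the next trial.

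**The concern.** A sample-size calculation needs an effect and an SD, and a small pilot estimates the two with very different precision. The SD is pinned down fairly well. The between-group difference may carry a standard error as large as any plausible effect. Because the required number per arm goes as one over the square of the effect, error in the effect is magnified.

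A pilot that overshoots by chance gives a next trial that is too small. One that undershoots gives an unaffordable trial, or the abandonment of a useful intervention. Supplying these inputs is one of the two purposes that Section 4.2 gives for the design, so the rule affects something the pilot is meant to deliver. The pilot's own comparison of the arms is not affected.

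**Working it through.** The plan gives no figure to reproduce: pilot size, effect, alpha and target power are all unstated.

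**Inputs.** From the documents: equal arms (6.3), a two-group comparison of change (9.4.1), and the observed difference and SD as sizing inputs (9.4.1). Assumed: pilot of n = 20, 30 or 50 per arm; true standardised difference d = 0.2, 0.3 or 0.5; next trial with two-sided alpha 0.05, 80% target power and no dropout.

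**1. Precision of the pilot difference.** In SD units, the standard error is √(2/n) and the 95% half-width is 1.96 × √(2/n).

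- n = 20: 1.96 × 0.316 = 0.62
- n = 30: 1.96 × 0.258 = 0.51
- n = 50: 1.96 × 0.200 = 0.39

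Except for d = 0.5 with 50 per arm, these are as large as the assumed effects or larger.

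**2. What the next trial needs.** Number per arm = 2 × (1.96 + 0.8416)² / d² = 15.70 / d². This gives 393, 175 and 63 per arm for d = 0.2, 0.3 and 0.5.

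**3. One illustration.** Take d = 0.3 and 20 per arm.

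- A pilot one standard error too high observes 0.3 + 0.316 = 0.616. The planned size is 15.70 / 0.616² ≈ 42 per arm. True power is Φ(0.3 × √(42/2) − 1.96) = Φ(−0.585) ≈ 28%.
- A pilot one standard error too low observes about −0.02, which gives no usable superiority sample size.

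The chance of an observed difference at or below zero is Φ(−0.3/√(2/n)), or 17%, 12% and 7% for 20, 30 and 50 per arm.

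**4. Full distribution.** In at least 200,000 simulated pilots per setting, the observed difference was drawn from a normal distribution with mean d and variance 2/n, and the SD from a chi-square with 2n − 2 degrees of freedom. The next trial was sized on the absolute observed ratio by the formula in step 2, and its power evaluated at the true d. Rounding n up or not moves the results by about one point. With the next trial always proceeding:

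| True d | Mean true power (n = 20 / 30 / 50) | Chance of under-sizing |
|---|---|---|
| 0.2 | 59% / 64% / 68% | 61% / 56% / 52% |
| 0.3 | 67% / 70% / 73% | 53% / 51% / 50% |
| 0.5 | 73% / 74% / 76% | about 50% throughout |

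At d = 0.3, true power falls below 50% in 36%, 32% and 26% of cases. With 20 per arm, planned size runs from about 30 to about 4,000 per arm (10th to 90th percentile) against the 175 needed.

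**5. Effect of selection.** If the next trial proceeds only when the difference favours the experimental arm, mean true power at d = 0.3 is about 62%, 67% and 71%. If it proceeds only when observed d exceeds 0.2, median true power at d = 0.3 is 45%, 52% and 60%. Neither rule is in the documents.

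**6. The alternative.** Fix the effect in advance at the true value and take only the SD from the pilot. Mean power is then 78–79%, with a 5th percentile of 62–70%. At d = 0.3 and 20 per arm, planned size spans only 126 to 228 per arm (10th to 90th percentile). Using the one-sided 80% upper limit for the SD multiplies it by √(df/χ²₀.₂) with df = 2n − 2: 1.116, 1.090 and 1.067. Squaring gives 1.24, 1.19 and 1.14 times the sample size, and under-sizing falls to about 18–20%.

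**The case against.** A reader might infer that the plan makes the next trial underpowered more often than not. The documents do not support that. It needs a rule for proceeding only after a promising result, and none is stated. Without one, under-sizing is near a coin flip (50–61% over the assumed range). The low medians of 45–60% belong to an assumed cut-off of 0.2 and a single assumed effect of 0.3; at d = 0.5 with 50 per arm the same cut-off gives roughly 77–78%.

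Frequency of under-sizing is also a weak measure. Sizing on the pilot SD with a fixed effect falls short about half the time too, though only slightly. What separates the two methods is the spread of planned sizes and the loss of mean power.

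A reader might also infer that the largest of the five differences will be used. The text does not say so; sizing on the most demanding measure would fit it equally well. Choosing the largest remains a risk: with a common d of 0.3, 20–50 per arm and correlations of 0 to 0.5, the largest of five would exceed the truth in 83–97% of pilots.

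Finally, Section 4.2 puts preliminary efficacy ahead of power inputs, and Section 9.4.1 does not exclude other inputs. Both points are fair. They limit how much weight the issue carries, but the stated rule still names the observed difference as an input with no allowance for its error.

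**Conclusion.** The point holds as one about instability and lost expected power. Followed as written, Section 9.4.1 would give a next-trial size that can be wrong many-fold in either direction. Mean true power would be some 4 to 21 percentage points below an 80% target (76% to 59%) even if the trial always proceeds, and the shortfall would grow if it proceeds only after a favourable pilot.

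These sizes depend on the assumed pilot size, effect, alpha and target power. The shortfall shrinks as the pilot or the true effect gets larger. Confidence is medium for that reason. This is a cheap improvement, not a flaw in the pilot's own comparison.

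**What to change.** Replace the last paragraph of Section 9.4.1 with:

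> The next trial will be sized on a smallest worthwhile difference for one named primary behaviour, fixed before any between-group outcome comparison is made, and not on the observed pilot difference. The pilot will supply the SD of change (using its one-sided 80% upper confidence limit), the pretest-to-follow-up correlation, retention and module completion. Pilot group differences will be reported with 95% confidence intervals.

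The timing is tied to the first between-group comparison because Section 6.3 says masking does not apply, so there is no unblinding date to use. The SD of change matches the planned t-test on change; use a baseline-adjusted SD only if the next trial's analysis is baseline-adjusted. Section 4.2 should be worded to match.

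The cost is one paragraph, agreement on the behaviour and its worthwhile difference, and a next trial about 14–24% larger than the point estimate of the SD would give (50 down to 20 per arm in the pilot). No new data are needed and conduct does not change.
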